1.3.2 Pharmacokinetic Endpoints

CSF samples are collected pre-dose on each injection day during the treatment period:

- Part 1: Days 1, 29, 57, and 85 for the 4-dose regimen, or Days 1 and 85 for the 2-dose regimen.
- Part 2: Days 1, 85, 169, 253, 337.

CSF samples are also collected during the Post-Treatment Period:

- Part 1: Days 113 and 141 for patients in Cohorts A and B, and Days 141 and 197 for patients in Cohorts C and D
- Part 2: Day 421

Plasma samples will be collected for PK analyses on the following days:

Part 1: Days 1, 2, 29, 57, 85, and 86, during the Treatment Evaluation Period and on Days 113, 141, 169, 197 (patients in Cohorts C and D only) and 253 during the Post-Treatment Period

Part 2: Days 1, 2, 85, 169, 253, 337, and 338 during the Treatment Evaluation Period and on Days 421 and 449 during the Post-Treatment Period

Plasma post-distribution drug levels will be measured. C_{max} and area under the curve (AUC) will be determined, and elimination half-life will be assessed where appropriate.

1.3.3 Exploratory Endpoints

All endpoints in the study, including the exploratory endpoints serve as safety measures. While the below endpoints will be monitored for evidence of target engagement or PD effect, they will also be monitored to ensure the patient does not experience unexpected worsening during the study.

- Key exploratory endpoints
 - o CSF total tau
 - Biochemical
 - Other potential CSF biomarkers may include, but are not limited to, target engagement (phospho-tau), A-beta42, A-beta40, neuronal injury markers (neurofilament light chain [NfL], phospho neurofilament heavy [pNfH], neuronal pentraxin, alpha-synuclein, visinin-like protein 1 [VILIP1]), synaptic markers (neurogranin [Ng], chromogranin B, synaptosomal-associated protein 25 [SNAP25]), innate immune activation markers (interleukin-6 [IL-6], tumor necrosis factor alpha [TNFα], interleukin-1 beta [IL-1β], monocyte chemoattractant protein-1 [MCP-1], S100B, chitinase-3-like protein 1 [YKL-40], complement [C3, factor H]), apolipoprotein E, clusterin, butyrylcholinesterase (BCHE), Potential blood/plasma biomarkers may include, but are not limited to NfL, pNfH, tau, IL-6, TNFα, 24S-hydroxycholesterol and uric acid
 - Neuroimaging
 - Structural MRI Volumetric Analysis
 - Hippocampal, whole brain, intracranial and ventricle volumes
 - Exploratory MRI Analyses
 - Perfusion analysis arterial spin labelling (ASL)
 - Diffusion analysis
 - Cortical thickness
 - White matter lesion analysis
 - CSF space analysis
 - o PET (Cohorts C and D only in Part 1, and all patients in Part 2)
- Clinical Evaluations
 - o Functioning/ability to perform activities of daily living
 - Functional Activities Questionnaire (FAQ)

- o Cognitive
 - Repeatable Battery for the Assessment of Neuropsychological Status (RBANS)
 - Mini-mental state examination (MMSE)
 - Clinical Dementia Rating (CDR) Scale
- Neuropsychiatric
 - Neuropsychiatric Inventory Questionnaire (NPI-Q)

Analyses may explore relationship between selected parameters (at baseline and their progression during the study) and genetic causes of AD (*APP*, *PSEN1*, *PSEN2*), potential genetic modifiers of disease phenotype (commonly occurring risk-associated SNPs of *APOE*, *BCHE*, *IL1RAP*, *CD33* and *MAPT H1* haplotype).

2. PROCEDURES

2.1 General Overview of Procedures

Ionis Pharmaceuticals, Inc. (or designee) will review all study data including source documents, CRFs, and laboratory reports. The study site will enter subject source data into the case report form. Safety laboratory data will be transferred electronically from Covance Central Laboratory Services, Inc. and Medpace Reference Laboratories to Ionis Pharmaceuticals, Inc. ECG data will be transferred electronically from BioClinica, Inc. to Ionis Pharmaceuticals, Inc. Cognitive and Neuropsychiatric scale data will be transferred electronically from MedAvante, Inc. to Ionis Pharmaceuticals, Inc. The exploratory image analysis data will be transferred electronically from Invicro, a Konica Minolta Company to Ionis Pharmaceuticals, Inc. The exploratory biomarker data will be transferred electronically from both Covance Central Laboratory Services, Inc. and Immunologix Laboratories to Ionis Pharmaceuticals, Inc.

2.2 Randomization & Treatment Allocation

In the MAD, Part 1, of the study, a patient will be randomized after all Screening assessments have been completed and after the Investigator has verified that the patient is eligible per criteria. No patient may begin treatment prior to randomization and assignment of a unique patient identification number.

Eligible patients will be randomized centrally by an automated system to receive ISIS 814907 or placebo. Within each cohort, randomization will be 3:1 ISIS 814907: placebo as outlined in Section 1.1.

The Sponsor or designee will prepare the randomization list.

In the LTE, Part 2, of the study, patients in Cohorts A and B will be registered after all Registration visit assessments for Part 2 have been completed and the Investigator has verified that the patient is eligible per criteria. Patients in Cohort C and D will transition seamlessly based

on the Part 1 eligibility criteria and do not need to be reassessed prior to the start of Part 2. In the LTE, Part 2, all eligible patients will be enrolled by an automated system to receive ISIS 814907. Patients will retain their patient identification number assigned in Part 1.

2.3 Conduct

The study will be conducted in accordance with current Good Clinical Practice (GCP) and International Conference on Harmonization (ICH) guidelines, the World Medical Association Declaration of Helsinki guidelines, the Food and Drug Administration (FDA) Code of Federal Regulations, and all other local regulatory requirements.

2.4 Data Monitoring

2.4.1 Safety Data Monitoring

Ionis Pharmaceuticals, Inc. (or designee) is responsible for processing all reported adverse events (AEs). All serious adverse events (SAEs), reported to Ionis Pharmaceuticals, Inc. (or designee), are reviewed per standard operating procedures. The medical monitor will review all AEs and SAEs on an ongoing basis throughout the study. Ionis Pharmaceuticals, Inc. (or designee) will prepare and submit safety reports to the health authorities worldwide in accordance with local requirements. If it becomes necessary to communicate new safety information, Ionis Pharmaceuticals, Inc. (or designee) will also prepare a safety notification letter and transmit it to the study sites.

2.5 Data Management

An electronic case report form (eCRF) utilizing an Electronic Data Capture (EDC) application will be used for this Study.

2.5.1 Case Report Form (CRF) Data

BioClinica (or designee) is responsible for creating the Electronic Data Capture (EDC) data entry screens, database and edit checks using definitions developed by Ionis Pharmaceuticals, Inc. Trennic Data Services has been contracted by Ionis Pharmaceuticals, Inc. and is responsible for the review, data management querying and locking of the database.

Data are single-entered into the EDC system by the clinical site staff. Programmed edit checks (computer logic that checks the validity of the data entered and prompts for missing data that is expected to be entered) are run and automatic queries are generated. Trennic Data Services reviews all data for accuracy and validity and generates additional queries in the EDC system when necessary. The data are corrected or an explanation concerning the query is provided in the EDC system. After all data are entered, reviewed (by Data Management and Clinical Development) and queried, and all queries resolved, the database is locked.

2.5.2 Laboratory Data

Ionis Pharmaceuticals, Inc. is responsible for the format of the laboratory electronic data transfers, transfer schedule and review of the clinical laboratory data. The safety laboratory data will be provided by Covance Central Laboratory Services, Inc. and Medpace Reference Laboratories, and stored as SAS data sets or Excel files. The exploratory CSF biomarker data will be transferred electronically from both Covance Central Laboratory Services, Inc. and Immunologix Laboratories to Ionis Pharmaceuticals, Inc. Data will be provided as SAS datasets.

2.5.3 Pharmacokinetics (PK) Data

Ionis Pharmaceuticals, Inc. is responsible for the management and review of the plasma, urine drug concentration data. This process involves reviewing the patient and visit identifiers (i.e., patient demographics) with the clinical data collected in the EDC system. The PK data are not stored in the EDC system.

2.5.4 Cognitive and Neuropsychiatric Data

MedAvante (or designee) is responsible for collecting and providing external cognitive and neuropsychiatric scale data to Ionis Pharmaceuticals, Inc. External scale datasets include Geriatric Depression Rating Scale (GDS) dataset, Modified Hachinski Ischemic Scale (MHIS) dataset, Mini-Mental State Examination (MMSE) dataset, Clinical Dementia Rating (CDR) dataset, Repeatable Battery for the Assessment of Neuropsychological Status (RBANS) dataset, Neuropsychiatric Inventory Questionnaire (NPI-Q) dataset, Functional Assessment Questionnaire (FAQ) dataset, Columbia Suicide Severity Rating Scale (C-SSRS) dataset. Data will be provided as SAS datasets provided via SAS transport files.

2.5.5 Exploratory Neuroimaging Data

Invicro (or designee) is responsible for transferring the exploratory image analysis data to Ionis Pharmaceuticals, Inc. The datasets include volumetric MRI analysis dataset, FDG-PET and Tau-PET quantitative analysis dataset, cortical thickness analysis dataset, white matter lesion volume analysis dataset, CSF space analysis dataset, diffusion analysis dataset and perfusion analysis dataset. The final file structure will be comma separated value (.csv) files.

3. ANALYTICAL PLAN

3.1 General Overview of Analyses

Descriptive summary statistics including number of patients, mean, median, standard deviation, standard error of mean, interquartile range (25th percentile, 75th percentile), and range (minimum, maximum) for continuous variables, and counts and percentages for categorical variables will be used to summarize most data. Where appropriate, p-values will be reported. All

statistical tests will be conducted using 2-sided tests with 5% Type I error rate unless otherwise stated.

PK parameters will be summarized by treatment group including number of patients, mean, standard deviation, coefficient of variation (CV), geometric mean, median, minimum, and maximum.

All eCRF data and data transfers from external vendors (e.g., laboratory, cognitive and neuropsychiatric testing) will be provided in the subject data listings. Patient data listings will be presented for all patients enrolled into the study.

Within this document, the terms 'patient' and 'subject' are both used to describe the individual who enrolls in this study. The terms 'MAD' and 'Part 1' may be used interchangeably. Similarly, the terms 'LTE' and 'Part 2' may be used interchangeably.

3.2 Analysis Periods, Analysis Groups, and Baseline definitions

The Analysis Periods, Analysis Groups (i.e. treatment groups), and Baseline definitions are given in the following sections. Please refer to Table B1, Table B2 and Table B3 in Appendix for more details.

3.2.1 Analysis Periods

There are four periods which will be used for analysis and are defined as:

- MAD Period: Analyses include data from MAD, Part 1.
- LTE Period: Analyses include data from LTE, Part 2.
- MAD+LTE Period: Analyses include integrated data from both MAD, Part 1 and LTE, Part 2, regardless of a subject's randomization assignment or LTE enrollment status. For example, a subject receiving MAD placebo treatment who does not enroll in LTE will still contribute data from the MAD to this analysis.
- Active Treatment Period: Analyses include data from study periods in which a subject receives active ISIS 814907 treatment. (Note: Study periods refer to Part 1 and/or Part 2, including post-treatment follow-up but excluding any variable gaps in time between Part 1 and Part 2 for subjects in Cohorts A and B). Data collected during a placebo dosing period are not included (except relevant baseline data). Subjects who receive MAD active treatment will contribute data regardless of LTE enrollment status. Subjects who receive MAD placebo treatment will only contribute data if enrolled and dosed in the LTE.

In general, listings will be created for the MAD Period and the MAD+LTE Period.

Safety, pharmacodynamic and exploratory analyses will be conducted for the MAD Period and the LTE Period separately.

The MAD+LTE Period will be used to analyze select biomarkers, neuroimaging and key clinical assessments:

- o MRI (exploratory)
- o Tau-PET/FDG-PET
- o CSF biomarkers including but not limited to total tau, phospho-tau and A-beta42
- o MMSE
- o RBANS
- o CDR

The Active Treatment Period will be used to analyze select safety endpoints including:

- Laboratory assessments: Potential clinically significant laboratory abnormalities, hepatotoxicity, and shift analyses
- o CSF Safety Panel
- o Safety MRIs
- o Incidence rates for treatment emergent adverse events (TEAEs) and serious TEAEs

3.2.2 Analysis Groups

The analysis groups are described below according to the analysis periods in which they will be used.

3.2.2.1 *MAD Period*

- Pooled Placebo (excluding PK analyses): Cohorts A, B, C and D placebo-treated patients
- ISIS 814907 10mg Q4W: 10 mg ISIS 814907-treated patients
- ISIS 814907 30mg Q4W: 30 mg ISIS 814907-treated patients
- ISIS 814907 60mg Q4W: 60 mg ISIS 814907-treated patients
- ISIS 814907 115mg Q12W: 115 mg ISIS 814907-treated patients
- Total Active ISIS 814907 (excluding PK analyses): Cohorts A, B, C and D
 ISIS 814907-treated patients

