| | Four (4) ascending dose level cohorts (A, B, C and D) of mild AD patients will be enrolled sequentially and randomized 3:1 to receive ISIS 814907 or placebo. Cohorts A and B will comprise 8 patients each, Cohort C will comprise 12 patients and Cohort D will comprise 16 patients. |
| | A sentinel dosing strategy will be implemented. The first 2 patients at a given dose level will be assigned 1:1 active:placebo, and at least 1 week must elapse between initiation of treatment in these 2 patients and initiation of treatment in additional patients at this dose level. The remaining patients will be assigned to active or placebo at a 5:1 ratio (cohorts with N = 8), 8:2 ratio (cohorts with N = 12), or 11:3 ratio (cohorts with N = 16) to ensure a 3:1 active:placebo balance in each cohort. During the study, PK and PD data will be compared to the ISIS 814907 levels and PD effects that are expected according to the preclinical PK/PD model. Based on these reviews, the dose level(s) and/or dosing interval for future cohort(s) may be adjusted. |

Study Design Continued

Multiple Ascending Dose Part of Study, Part 1 Continued

Each patient will receive 4 doses of Study Drug with a 28-day interval between doses. In the event of a dosing interval change for Cohort D, each patient will receive 2 doses of Study Drug with an 84-day interval between doses. Patients not completing the intended course of all Study Drug administrations may be replaced up to a limit of 25% of the cohort sample and only if their treatment assignments remain blinded and if the reason for premature discontinuation from the Treatment Evaluation Period does not involve a dose-limiting toxicity (DLT).

Patients in Cohorts A and B will complete all visits up to Day 253 in Part 1 and will enter Part 2 of the study after the FSMG has reviewed the Part 1 Cohort C data during the dose-escalation meeting to Cohort D; there will be a variable gap of time between the end of Part 1 and entry into Part 2 for those patients. Patients in Cohorts C and D will seamlessly transition from Part 1 into Part 2 after completing all visits up to Day 253 in Part 1. This visit will correspond to Day -1 in Part 2.

Patients who discontinue Study Drug in the Treatment Evaluation Period of Part 1 should complete any follow-up visits associated with the most recent administration of Study Drug (see Section 8.9) and should complete the Part 1 Post-Treatment Period.

Long-Term Extension Part of Study, Part 2

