 - Mini-mental state examination (MMSE)
- Neuropsychiatric
 - Neuropsychiatric Inventory Questionnaire (NPI-Q)

Analyses may explore the relationship between parameters and genetic causes of AD (APP, PSEN1, PSEN2) or potential genetic modifiers of disease phenotype (commonly occurring risk-associated SNPs of APOE, BCHE, IL1RAP and MAPT H1 haplotype)

Statistical Considerations

While there is no statistical basis for the sample size, it has been selected based on prior experience with generation 2 ASOs given by IT bolus injection to ensure that the safety, tolerability, PK, and exploratory pharmacodynamics will be adequately assessed while minimizing unnecessary patient exposure.

Multiple Ascending Dose, Part 1

Placebo-treated patients will be pooled for analysis. The safety and tolerability of ISIS 814907 will be assessed by determining the incidence, severity, and dose-relationship of AEs and changes in laboratory parameters and other safety measures by dose. Safety results in patients dosed with ISIS 814907 will be compared with those from patients dosed with placebo. If CSF total tau protein level is reflective of target engagement, exploratory analyses will be conducted to characterize the relationship between dose, CSF PK, and reduction from baseline in CSF total tau protein level. Analyses of biomarker and clinical evaluations will include dose- and PK-dependent effects and comparisons between patients receiving ISIS 814907 and those receiving placebo. The impact of reported genetic modifiers of disease phenotype on study endpoints may be investigated.

Long-Term Extension, Part 2

Longer-term safety and tolerability of ISIS 814907 will be assessed by determining the incidence, severity, and dose-relationship over time of AEs and changes in laboratory parameters and other safety measures by dose and CSF PK. Exploratory analyses will be conducted to characterize the relationship between dose, CSF PK, and reduction from baseline in CSF total tau protein level over time. Analyses of biomarker and clinical evaluations will include dose- and PK-dependent effects and comparisons between patients receiving ISIS 814907 in both Parts 1 and 2 of the study, and those receiving placebo in Part 1 followed by ISIS 814907 in Part 2.

Sponsor

Ionis Pharmaceuticals, Inc.

STUDY DESIGN AND TREATMENT SCHEMA FOR MAD, PART 1

SCREENING PERIOD

Days -57 to -2 (Weeks -8 to -1)

Collect informed consent then assess patient eligibility

TREATMENT EVALUATION PERIOD

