Initiation of dosing in a new cohort began after 3 conditions had been met: (1) all patients in the lower-dose cohorts have been enrolled, (2) at least 2/3 of the patients in the lower-dose cohort had been followed for at least 7 days after receipt of the fourth dose of Study Drug, and (3) a review of data (safety, PK, and PD data) collected in the lower-dose cohorts had been conducted by the Formal Safety Monitoring Group (FSMG) and a decision had been made to proceed with the next cohort.

Each patient in cohorts A, B and C received 4 doses of Study Drug with a 28-day interval between doses. In cohort D, the protocol prespecified 2 dosing regimen options: 1) four doses of Study Drug at 90 mg with a 28-day interval between doses or 2) two doses of Study Drug at 115 mg with an 84-day interval between doses. The FSMG selected the 115 mg x 2 dosing regimen. The planned dose regimens for the study are shown below. Based on emerging safety data from this study, the protocol permitted one or more cohorts to expand and enroll additional patients. PK and PD measures were collected at each dose level and compared to the results predicted by models constructed from preclinical data.

Cohort A: N = 8, mild AD, 10 mg ISIS 814907 or placebo \times 4 doses

Cohort B: N = 8, mild AD, 30 mg ISIS 814907 or placebo \times 4 doses

Cohort C: N = 12, mild AD, 60 mg ISIS 814907 or placebo \times 4 doses

Cohort D: N = 16, mild AD, 90 mg ISIS 814907 or placebo \times 4 doses or 115 mg ISIS 814907 or placebo \times 2 doses

Following the 3-month Treatment Period, there was a 6-month Post-Treatment Period.

Long-Term Extension, Part 2

The ability for participants completing the MAD, Part 1, of the study to enter an open-label LTE, Part 2, of the study started with Cohort C. All patients in Cohorts C and D could seamlessly transition from Part 1 to Part 2. For patients in Cohorts C and D, Day 253 in Part 1 corresponded to Day -1 in Part 2. In Part 2, the Treatment Evaluation Period of 48 weeks was followed by a Post-Treatment Period of 16 weeks, except in the UK (Amendment 7) where the Post-Treatment Period was 23 weeks.

All patients will receive ISIS 814907 in Part 2 and will be dosed at an 84-day interval, regardless of the dose interval utilized in Part 1.

- Cohort C patients will continue the Cohort C dose (60 mg) with a quarterly (84-day) dose interval in the LTE, Part 2

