3.5.3 Adverse Events

3.5.3.1 MAD Period and LTE Period

The incidence (proportion) of treatment-emergent adverse events (TEAEs) will be summarized for the MAD and LTE Periods separately, and incidence (rates) of TEAEs will be summarized for the Active Treatment period where indicated by *. The Medical Dictionary for Regulatory Activities (MedDRA) version 20.0 will be used. Summaries will be presented by preferred term (PT) and system organ class (SOC), unless otherwise indicated, for:

- Any TEAE* (summarized by PT only and by both SOC and PT)
- TEAEs potentially related to Study Drug. Related is defined as "Related", "Possible", or missing relationship to study drug, as determined by the investigator
- TEAEs potentially related to Lumbar Puncture (LP) procedure. Related is defined as "Related", "Possible", or missing relationship to LP procedure
- Any TEAE by severity*. At each level of subject summarization, a subject is classified according to the highest severity if the subject reported one or more events. TEAEs with missing severity will be categorized as "Missing" for this summary
- TEAEs potentially related to Study Drug by severity
- TEAEs potentially related to LP procedure by severity
- Serious TEAEs* (by PT only and by both SOC and PT)
- Serious TEAEs potentially related to Study Drug*
- Serious TEAEs potentially related to LP procedure*
- TEAEs leading to permanent study drug discontinuation* (by PT only and by both SOC and PT)

The number and proportion of LPs leading to TEAEs will be summarized for the MAD and LTE Periods separately. The severity of AEs and SAEs will be graded based on criteria from the Common Terminology Criteria for Adverse Events (CTCAE) Version 4.03, June 2010. SAEs and non-serious AEs that lead to permanent study drug discontinuation will be listed separately. Non-treatment emergent adverse event will be flagged in the data listing.

An adverse event will be regarded as treatment emergent if it is present prior to receiving the first dose of study drug (MAD: ISIS 814907 or placebo; LTE and Active Treatment Periods: ISIS 814907) and subsequently worsened, or is not present prior to receiving the first dose of

study drug (MAD: ISIS 814907 or placebo; LTE and Active Treatment Periods: ISIS 814907) but subsequently appeared.

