Laboratory tests to ensure patient safety include clinical chemistry panel, hematology panel, coagulation, urinalysis and safety CSF labs (Red blood cells, WBC, Glucose, and Protein), will be summarized by treatment group and each post-baseline visit for the MAD and LTE Periods separately. These safety variables will also be presented as change and percent change from baseline over time after Study Drug administration, as appropriate.

In addition, shift tables will be done for the MAD, LTE, and Active Treatment periods. The shifts (relative to the normal range) from baseline to the minimum and maximum post-baseline values, or shifts to abnormal, as appropriate, for each specific laboratory parameter in the following categories: CSF safety panel, coagulation, hematology, chemistry, and urinalysis (excluding microscopic examination) will be presented. If a subject is missing a baseline value but had a post-baseline value, then the baseline assessment is labeled as "unknown". Likewise, if a subject had a baseline value but had no post-baseline values, then the minimum and maximum are labeled as "unknown". For each parameter, the incidence of shift to low will be summarized using the minimum post-baseline values; the incidence of shift to high will be summarized using the maximum post-baseline values.

Only central laboratory data will be used for the summary tables and figures. Local laboratory data will be provided in the listings only, except for local results for CSF safety tests which will be listed and summarized in tables.

Individual data listings of all laboratory results for MAD Period and MAD+LTE Period will be presented for each subject. All values outside the clinical reference ranges will be flagged in the data listings. The abnormal value is defined as the value below the lower limit or above the upper limit of the clinical reference range. Abnormal laboratory results for the MAD and MAD+LTE Periods will also be displayed in separate listings.

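### The single pooled-placebo group in Part 1 mixes two lumbar-puncture schedules, so per-patient tables of LP-driven adverse events and CSF safety shifts are not schedule-matched at any single dose

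*Combined protocol and SAP*

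**What the plan says.** SAP 3.2.2.1 sets up the MAD Period groups: one column per dose, Total Active, and a single Pooled Placebo group made of "Cohorts A, B, C and D placebo-treated patients". It is used for all MAD analyses except PK. Protocol 10.6 gives the reason: few placebo patients per cohort.

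The regimens differ. SAP 1.1 records that "The FSMG selected the 115 mg x 2 dosing regimen", so Cohort D was dosed on Days 1 and 85, while Cohorts A-C were dosed on Days 1, 29, 57 and 85. Protocol 8.1 has an LP at every dosing visit.

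On outcomes, SAP 3.5.3.1 states: "The incidence (proportion) of treatment-emergent adverse events (TEAEs) will be summarized for the MAD and LTE Periods separately". For laboratory panels, including the CSF safety panel, SAP 3.5.6 uses worst values: "the incidence of shift to high will be summarized using the maximum post-baseline values", with the minimum used for shifts to low. The protocol synopsis (Statistical Considerations) intends a placebo comparison: "Safety results in patients dosed with ISIS 814907 will be compared with those from patients dosed with placebo".

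SAP 3.5.3.1 also tabulates LP-related events separately and plans a count and proportion of LPs that lead to an event in the MAD Period. It does not say that this summary is split by analysis group.

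**The concern.** A proportion of patients with at least one event, or a patient's most extreme value over follow-up, rises with the number of procedures or samples, even with an inert drug. If the placebo column has more LPs than the 115 mg column and fewer than the other three dose columns, the error has opposite signs on the two sides. Differences from placebo would be too favourable at the top dose and too unfavourable at the lower doses.

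The primary objective is safety across ascending doses, and the synopsis asks for the dose relationship of adverse events. For LP-type events and CSF findings, an artefact in that direction could hide or flatten a real gradient. The protocol treats LP effects as real: section 8.4 monitors post-LP headache, and section 3.8 excludes known LP effects from dose-limiting toxicity.

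**Working it through.** **Allocation.** The synopsis gives the sizes: "Cohorts A and B will comprise 8 patients each, Cohort C will comprise 12 patients and Cohort D will comprise 16 patients". It adds: "The first 2 patients at a given dose level will be assigned 1:1 active:placebo"; the rest follow a "5:1 ratio (cohorts with N = 8), 8:2 ratio (cohorts with N = 12), or 11:3 ratio (cohorts with N = 16"). Placebo is therefore 1+1, 1+1, 1+2 and 1+3 = 2, 2, 3, 4 (total 11). Active is 1+5, 1+5, 1+8 and 1+11 = 6, 6, 9, 12 (total 33). The sum is 44, the protocol's planned number. Seven planned placebo patients are on the 4-dose schedule and four on the 2-dose schedule.

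**Procedures from Day 1 (Protocol Appendix A.1-A.3).** The Day 253 LP is only for patients who missed an earlier sample and is not counted.
- Cohorts A and B: LPs on Days 1, 29, 57, 85, 113 and 141 = 6.
- Cohort C: Days 1, 29, 57, 85, 141 and 197 = 6.
- Cohort D: Days 1, 85, 141 and 197 = 4.
- The Day 1 pre-dose sample is baseline, so post-baseline CSF safety samples are 5, 5, 5 and 3.

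**Pooled placebo averages.**
- LPs from Day 1: (7×6 + 4×4)/11 = 58/11 = 5.27; 5.27/4 = 1.32.
- Including the screening LP: (7×7 + 4×5)/11 = 69/11 = 6.27; 6.27/5 = 1.25.
- CSF samples: (7×5 + 4×3)/11 = 47/11 = 4.27, against 3.

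The count from Day 1 is the relevant one for treatment-emergent events. Total Active is balanced against the pool: 12/33 and 4/11 are both 36% on the 2-dose schedule. The mismatch is in the single-dose columns.

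**Size of the tilt with no drug effect.** The documents give no risk per LP or per sample, so p is assumed and occasions are taken as independent. P(at least one) = 1 − (1 − p)^k, with k = 4 or 6 LPs and 3 or 5 samples. Pooled placebo = (7 × 4-dose value + 4 × 2-dose value)/11.

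| Outcome | p | 115 mg | Pooled placebo | 10/30/60 mg | 115 mg − placebo | 10/30/60 mg − placebo |
|---|---|---|---|---|---|---|
| LP event | 5% | 18.6% | 23.6% | 26.5% | −5.1 | +2.9 |
| LP event | 10% | 34.4% | 42.3% | 46.9% | −7.9 | +4.5 |
| LP event | 20% | 59.0% | 68.4% | 73.8% | −9.4 | +5.4 |
| CSF shift | 5% | 14.3% | 19.6% | 22.6% | −5.3 | +3.0 |
| CSF shift | 10% | 27.1% | 35.9% | 41.0% | −8.8 | +5.0 |
| CSF shift | 20% | 48.8% | 60.5% | 67.2% | −11.7 | +6.7 |

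For LP events, −9.4 is close to the largest value the model can give (reached near p = 18%).

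**Against sampling error.** At p = 10% per LP, the standard error of 115 mg minus pooled placebo is √(0.344×0.656/12 + 0.423×0.577/11) = 20.2 points. The same formula gives about 16 to 21 points across the table.

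**Replacing the pool with Cohort D placebo (n = 4).** At p = 10% per LP the bias is zero, but the standard error is √(0.344×0.656×(1/12 + 1/4)) = 27.4 points. The pool's total error, bias included, is √(20.2² + 7.9²) = 21.7 points.

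**The case against.** **Pooling is the more accurate single estimator.** The pool has the smaller total error under the same assumptions (21.7 versus 27.4 points), and one patient moves a 4-patient column by 25 points. This stands, and it rules out substituting the Cohort D column for the pool.

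**Much is already planned.** LP-related events have their own tables, a per-LP summary is foreseen, CSF safety results are also shown by visit (Days 85 and 141 are common to all cohorts), patient listings are provided, and no between-group adverse-event test is specified. This stands in part. The LP-related table is still per patient and depends on attribution, the per-LP summary is not stated to be by group, and no per-sample CSF figure is planned. The patient-year rates in SAP 3.5.3.2 cover only the Active Treatment Period, which excludes placebo-period data.

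**The size is assumed.** This stands. If some patients are simply prone to LP events, events cluster within them and the tilt shrinks.

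**Splitting placebo leaves the active columns unequal.** True: 6 LPs remain set against 4. Only differences from placebo become matched, which is why per-LP and per-sample figures are also needed.

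**Stronger readings.** A reader might infer that top-dose safety in general looks better than it is. The documents do not support that. Scheduled ECGs match across cohorts, and post-baseline chemistry and hematology draws number 8 in Cohorts C and D and 7 in A and B. Contacts at which adverse events are recorded do differ (23 in A and B, 24 in C, 16 in D, Day 1 to Day 253). However, events are recorded continuously, whether observed or volunteered, and follow-up ends at Day 253 in every cohort, so a bias from contacts is possible but not shown. A reader might also take 115 mg to be the dose carried forward, but Part 2 continues both 60 mg and 115 mg. Nor is the separate Late Start D group in the extension an inconsistency: those patients receive a different extension dose.

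**Conclusion.** The point holds for two outcome types in the MAD Period: LP-driven treatment-emergent events, and minimum or maximum post-baseline CSF safety shifts. For these, the per-patient columns favour 115 mg and disfavour 10, 30 and 60 mg relative to pooled placebo, with no drug effect needed. The exposure imbalance follows directly from the planned schedule and allocation; replacements or missed LPs would change it slightly. Its effect on proportions, about 5-9 points for LP events and 5-12 points for CSF shifts at 115 mg, depends on the assumed 5-20% risks and on independence. That is below the sampling error and would rarely decide a conclusion alone. It is still systematic, its direction is known, and data already collected can show it. Comparisons of Total Active with pooled placebo are unaffected at the planned numbers.

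**What to change.** Keep Pooled Placebo as the main comparator and amend the SAP as follows.

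1. In the MAD treatment-emergent event tables (any, by severity, LP-related) and the CSF safety-panel shift tables, add supplementary placebo columns by schedule: Cohorts A-C (planned n = 7) and Cohort D (planned n = 4).
2. State that the planned number and proportion of LPs leading to events is reported by analysis group.
3. Add CSF safety abnormalities per sample, by analysis group.
4. Read any dose-relationship statement on LP-type events or CSF shifts alongside these exposure-adjusted figures, not from the pooled per-patient columns alone.

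The cost is SAP wording, two extra columns in a few tables and one short per-sample summary. No new data are needed. The Cohort D placebo column will be very imprecise and should be labelled as supplementary.
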